Individuals who are identified with AF or other actionable rhythm in the monitored cohort will be contacted, as well as their most appropriate provider with the individual's permission) with the diagnosis and necessary documentation.

5. Data Acquisition, Storage and Analysis

Rhythm analysis of ZIO XT Patches will occur as routine through iRhythm. Amiigo will carry out rhythm detection via the wristband monitor, and if AF suspected at a time when the individual is not also wearing a ZIO XT Patch, the individual will be sent another ZIO XT Patch and concurrent monitoring with a ZIO XT Patch will be repeated. Complete rhythm data for all individuals will be transferred to STSI for over read by the data adjudicating committee.

Participants and their identified primary provider will be contacted when necessary including all new diagnoses of AF or any other potentially clinically significant rhythms as determined by the adjudication committee. In these instances participants and their provider will be sent copies of full disclosure iRhythm reports.

Results of monitoring will be aggregated at STSI based on study ID number. These data will be periodically securely sent to Aetna for aggregation with all clinical data routinely available to

them. Aetna will generate and securely transfer to STSI the de-identified data sets necessary for endpoint analysis by STSI for all primary and secondary endpoints.

Future research

Subject information will be kept for up to 6 years after completion of this study for future research that has not yet been planned. De-identified information will be kept indefinitely for future research studies at Scripps Translational Science Institute.

6. Efficacy and Safety Endpoints

Primary Efficacy Endpoint

Incidence of newly diagnosed atrial fibrillation (as defined by \geq 30 seconds of atrial fibrillation or flutter, or a new clinical diagnosis) at the end of the 4-month monitoring period, comparing the monitored cohort (n=1000) with the delayed monitoring cohort (n=1000) as the primary analysis, and the observational cohort (n=4000) as a secondary analysis.

Secondary Efficacy Endpoints

1. Incidence of atrial fibrillation in the monitored cohort (n=2000) versus the observation control cohort (n=4000) at 12 months.
 - Rate of initiation of anticoagulation therapy in monitored compared with controls.
 - Differences in healthcare utilization based on claims data in the overall population as well as AF diagnosed individuals only.

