2. Time to first event of stroke, systemic emboli, or myocardial infarction in the sub-population of individuals diagnosed with AF in the 2 cohorts, as well as within the entire cohorts during 3 years of follow-up. For the Medicare population in who reliable mortality data are available the time to first event of stroke, systemic emboli, myocardial infarction or death will also be evaluated.
 - Time to first event of individual components of the combined endpoint.

3. Cost effectiveness outcome is a key analysis but because of the many unknowns surrounding event rates, and changes in therapy at the time of diagnosis a Bayesian approach seems most appropriate. The initial determination of cost effectiveness will be limited to those diagnosed with AF by 3 years using available claims data. A secondary analysis can evaluate the entire study population comparing a monitored approach to standard of care.
4. Exploratory analysis of the efficacy of the Amigo wristband in detecting AF relative to ECG confirmation by ZIO XT Patch.

Safety Endpoints

1. Incidence of hospitalization for a primary bleeding diagnosis.
2. Incidence of the detection of non-AF, but other actionable heart rhythm issues during monitoring.
3. Incidence, timing and etiology of early discontinuation of active monitoring.

Endpoint Data Dictionary

1. Atrial Fibrillation/Flutter: Diagnosis of atrial fibrillation or atrial flutter confirmed via the Aetna Informatics Health Profile Database (HPD). The HPD is a foundation database used to identify Aetna members with chronic diseases or medical conditions. The identification algorithms are comprised of medical, pharmacy, and clinical laboratory data from physician claims and encounters, specialist claims, pharmacy, facilities, laboratories and others.
2. Each of the end-points listed below will be identified using ICD9/ICD10 codes within the adjudicated inpatient or ER medical case.
 - a. Transient ischemic attack / Stroke
 - b. Myocardial infarction
 - c. Arterial thromboembolism
3. Hospital admitting, discharge and transfer (ADT) information will be used to identify hospitalizations, and length of stay.

4. Drug NDC codes will be used to identify new refill for any anticoagulant (dabigatran, rivaroxaban, apixaban) or P2Y12 antagonists (clopidogrel, prasugrel or ticagrelor).
5. Mortality will be determined based on the latest Aetna membership tables and hospital discharge status.

7. Statistical Considerations

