3. ANALYSIS OBJECTIVES

The analysis objectives corresponding to the study objectives listed in 1. INTRODUCTION AND BACKGROUND are the following:

Primary Analysis

1. Compare incidence of newly diagnosed atrial fibrillation (as defined by ≥ 30 seconds of atrial fibrillation or flutter detected by device, or a new clinical diagnosis recorded in claims data) at the end of the 4-month monitoring period in the immediate monitoring cohort (n=1,000) with delayed monitoring cohort (control group) (n=1,000) using ICD-9/ICD-10 codes.

Secondary Analyses

1. Compare time to first event of newly diagnosed atrial fibrillation (as defined by ≥ 30 seconds of atrial fibrillation or flutter detected by device, or a new clinical diagnosis recorded in claims data) at the end of the 4-month monitoring period in the immediate monitoring cohort (n=1,000) with delayed monitoring cohort (control group) (n=1,000) using ICD-9/ICD-10 codes.
2. Compare incidence of newly diagnosed atrial fibrillation (as defined by ≥ 30 seconds of atrial fibrillation or flutter detected by device, or a new clinical diagnosis recorded in claims data) at the end of the 4-month monitoring period in the immediate monitoring cohort (intervention group) (n=1,000) with delayed monitoring cohort (control group) (n=1,000) using HPD definition.
3. Compare prevalence of atrial fibrillation in the actively monitored cohort (n=2,000) with the matched observational control cohort (n=4,000) at 12 months.
4. Compare time to event of newly diagnosed atrial fibrillation in the actively monitored cohort (n=2,000) with the matched observational control cohort (n=4,000) at 12 months.
5. Compare the rate of initiation of anticoagulation therapy in the actively monitored cohort with the matched observational control cohort at 12 months.
6. Compare the rate of initiation of other atrial fibrillation-related therapies (antiarrhythmic agents excluding beta-blockers and calcium channel blockers, cardioversions, ablation procedures or hospitalizations with a primary diagnosis of AF) in the actively monitored cohort with the matched observational control cohort at 12 months.
7. Compare utilization in actively monitored cohort with the matched observational cohort at 12 months.
8. Compare time to first event of the combined endpoint of stroke, systemic embolism, or myocardial infarction in the actively monitored cohort with the matched observational control cohort at 3 years:

- a. In the entire cohorts.

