5. ENDPOINTS AND COVARIATES

[Data source in brackets]

Primary Endpoint

1. Atrial Fibrillation/Flutter: new diagnosis of atrial fibrillation or atrial flutter defined as:
 - a. ≥ 30 seconds of atrial fibrillation or flutter diagnosed and adjudicated on the iRhythm output (monitored cohort) [PI Diagnosis Database]
 - i. Date
 - ii. Duration
 - b. Claim for atrial fibrillation/atrial flutter with ICD-9 code 427.1 or 427.2 or ICD-10 code I48.91 or I48.9 [Aetna Claims Data; Aetna Medical Case]
 - i. Date

Secondary Endpoints

1. Atrial Fibrillation/Flutter: HPD algorithm [Aetna HPD Database]
2. Anticoagulation: Drug NDC codes for new refill for any:
 - a. Anticoagulant (dabigatran, rivaroxaban, apixaban) or
 - i. Date
 - b. P2Y12 Antagonists (clopidogrel, prasugrel or ticagrelor) without a new diagnosis of acute coronary syndrome
 - i. Date
4. Other AF-related therapies (i.e. antiarrhythmic agents excluding beta-blockers and calcium channel blockers, cardioversions, ablation procedures or hospitalizations with a primary diagnosis of AF)
5. UtilizationCommented [[name]]: Need to further define
3. Stroke-related visits during follow-up [Aetna Medical Case]
 - a. Inpatient
 - b. ER
 - c. Time to first stroke-related event (Inpatient or ER)
4. Myocardial infarction-related visits during follow-up [Aetna Medical Case]
 - a. Inpatient
 - b. ER
 - c. Time to first myocardial infarction-related event (Inpatient or ER)
5. Systemic thromboembolism-related visits during follow-up [Aetna Medical Case]
 - a. Inpatient
 - b. ER
 - c. Time to first systemic thromboembolism-related event (Inpatient or ER)
6. Death (Medicare population): [Aetna ATV; Aetna Membership Table]
 - a. Time to death (within 1 month of date)

- b. Cause of death
- 7. All-Cause Hospital Admissions [Aetna Medical Case]
 - a. Total number
 - b. Total length of stay
 - c. Individual admissions
 - i. Primary diagnosis
 - ii. Date
 - iii. Length of stay

Safety Endpoints

- 1. Hospital admission for primary bleeding diagnosis: [Aetna]
- 2. Incidence of non-AF, but other actionable heart rhythms captured by device (and confirmed by PI) [PI Diagnostic Database]
 - a. Atrial Tachycardia with variable block of > 30 seconds
 - b. Ventricular Tachycardia >5 beats
 - c. Pauses \geq 5 seconds
 - d. AV block
- 3. Early discontinuation of active monitoring in monitored cohort [Scripps Study Database]
 - a. Date of discontinuation
 - b. Cause of discontinuation

Exploratory Endpoint (Amiigo)

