The primary analysis will compare the proportion of subjects newly diagnosed with atrial fibrillation (numerator) per number of total number of subjects in the randomized group (denominator) during the first 4 months of the study between the immediate monitoring (intervention group) and delayed monitoring (control) groups using Fisher's exact test. Multivariable analysis of the primary outcome will also be performed using binomial multivariable logistic regression models to include baseline demographic (age, sex, race/ethnicity, median household income, geography, insurance type), and co-morbidity covariates. The primary analysis will be conducted with the endpoint (AF/atrial flutter) defined by any event in the Aetna databases with the ICD-9/ICD-10 code for AF/atrial flutter. Secondary analysis will be conducted using the same methods with the AF/atrial flutter endpoint defined by the HPD.

Intention-to-treat analysis will include all subjects who were randomized to the immediate monitoring or delayed monitoring groups and follow-up for outcomes from the device and the Aetna databases will be from date of enrollment to time of completion of monitoring with final patch or 4 months following enrollment, whichever is longest.

A per-protocol analysis will also be performed which will be limited to subjects in the immediate monitoring group who has a Zio patch reading of a total of at least 30 minutes and all subjects randomized to the delayed monitoring group.

Analysis of Matched Observational Cohort Study—12 month Follow-up

Analyses for the Matched Observational Cohort Study will involve comparison of outcomes in the actively monitored group from the randomized controlled trial (intervention = exposure to Zio patch monitoring) and the matched controls. Analysis at 12-month follow-up will include

the outcomes of new atrial fibrillation diagnosis and new prescriptions for 1) anticoagulants and 2) other AF-related medications.

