The analysis will compare the proportion of subjects with newly diagnosed atrial fibrillation (numerator) per number of total number of subjects in group (denominator) during the first 12 months from the date of enrollment of the actively monitored subject between the actively monitored cohort and matched observational cohort using Fisher's exact test. Multivariable analysis of the AF/atrial flutter outcome will also be performed using binomial multivariable logistic regression models to include baseline demographic (age, sex, race/ethnicity, median household income, geography, insurance type), co-morbidity covariates. The same analysis will be performed for the other 12-month follow-up outcomes of new prescription for anticoagulation medication and new prescription of other AF-related medications. All analyses will be conducted first as intention-to-treat and second among the per-protocol population.

Matched Observational Cohort Study – 3 year Follow-up

Analyses at 3 years of follow up will focus on time to event for disease outcomes (stroke, myocardial infarction, and systemic thromboembolism) and hospitalizations (all-cause and for bleeding) compared between the actively monitored cohort and the matched observational control cohort after 3 years of follow-up. Bivariate time-to-event analysis will be conducted using Kaplan-Meier analysis with the time to event calculated from the date of the enrollment of the actively monitored subject and the date of the first event of the specific disease outcome (separate analysis for each outcome). Subjects not having an endpoint event during the observation period will be censored at the end of the 3-year follow-up or date of discontinued enrollment from Aetna. Multivariable analyses will be conducted using Cox proportional hazard models and will include potential confounders including age, sex, race/ethnicity, insurance type, variables related to geography and co-morbidity scores. For the Cox models, if assumptions of proportionality are not met (as assessed by Kaplan-Meier and plots of Schoenfeld residuals), models accounting for non-proportionality (using time*covariate interaction terms) will be run.

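### The only coded definition of anticoagulation initiation leaves out warfarin and counts P2Y12 antiplatelet fills, so secondary analysis 5 would not report the anticoagulation start rate

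*SAP*

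**What the plan says.** The quantity to be estimated is clear. SAP section 3, Secondary Analysis 5 reads "Compare the rate of initiation of anticoagulation therapy in the actively monitored cohort with the matched observational control cohort at 12 months". Protocol section 6, under Secondary Efficacy Endpoint 1, has "Rate of initiation of anticoagulation therapy in monitored compared with controls", and the Objectives in protocol section 3 agree.

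SAP section 7 names the 12-month drug outcomes by class only: "new prescriptions for 1) anticoagulants and 2) other AF-related medications" and, in the analysis paragraph, "new prescription for anticoagulation medication and new prescription of other AF-related medications". It gives no drug list.

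The list is in SAP section 5, Secondary Endpoint 2. Its heading is "Anticoagulation: Drug NDC codes for new refill for any". Limb a is "Anticoagulant (dabigatran, rivaroxaban, apixaban) or" and limb b is "P2Y12 Antagonists (clopidogrel, prasugrel or ticagrelor) without a new diagnosis of acute coronary syndrome". Item 4 of the Endpoint Data Dictionary in protocol section 6 has the same six drugs but no exception for acute coronary syndrome: "Drug NDC codes will be used to identify new refill for any anticoagulant (dabigatran, rivaroxaban, apixaban) or P2Y12 antagonists (clopidogrel, prasugrel or ticagrelor".

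Two other places matter. The protocol's Background (section 2) describes oral anticoagulation as warfarin or a novel agent. The Other Endpoints in SAP section 5 list follow-up fills of P2Y12 inhibitors (item 73), novel anticoagulants (75), other anticoagulants (76), warfarin (77) and heparin (78) as separate fields. Nothing ties these fields to Secondary Analysis 5.

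**The concern.** The coded endpoint and the named endpoint differ in two ways.

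- **Warfarin is missing.** This is the firm defect. The protocol itself counts warfarin as oral anticoagulation, yet a participant who starts it after a screening diagnosis is scored as not having started anticoagulation.
- **An antiplatelet fill is enough.** The two limbs are joined by an *or* under one anticoagulation heading, so a P2Y12-only start without a new acute coronary syndrome is scored as an event. The exception suggests the limb may be deliberate. Even so, a composite with antiplatelets is not initiation of anticoagulation, and it would still leave warfarin out.

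Analysis 5 is the planned measure of whether screening changes anticoagulation, the step that links detection to the hoped-for outcome benefit. Analysis 6 also looks at treatment change, but through antiarrhythmics, procedures and AF hospitalization. If analysis 5 misses true starts and adds events of another kind, both the rates and the contrast are hard to interpret.

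A lesser gap is that no fill-free look-back period is given for a fill to count as new. The exclusion of chronic anticoagulation is rechecked at enrollment for randomized subjects, and controls are drawn from a pool with monthly eligibility updates. That leaves a missing detail, not the main problem.

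**Working it through.** The plan states no rate, power or sample size for this endpoint, so there is no figure to reproduce. The check is first a comparison of definitions and then an illustration of size.

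**Definitions side by side**

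| First fill after the start date | Named outcome (SAP section 3, analysis 5) | Coded outcome (SAP section 5, endpoint 2) |
|---|---|---|
| Dabigatran, rivaroxaban, apixaban | event | event |
| Warfarin | event | no event |
| P2Y12 antagonist only, no new acute coronary syndrome | no event | event |

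The second and third rows disagree. The coded rate therefore departs from the start rate unless neither kind of fill occurs or the two happen to cancel.

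**Illustration**

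From the plan (SAP section 7, Sample Size Determinations): AF at 12 months 7% monitored and 2% control; cohorts of 2,000 and 4,000.

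Assumed, because the documents give no figures: *t*, share of AF cases started on an anticoagulant; *w*, warfarin share of those starts; *p*, P2Y12-only starts; *q*, anticoagulant starts for reasons other than AF; *wq*, warfarin share of those. No one starts both classes.

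- Named rate = AF × t + q
- Coded rate = AF × t × (1 − w) + q × (1 − wq) + p

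*Base case: t = 50%, w = 20%, p = 1% in each cohort, q = 0.*

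- Named: 0.07 × 0.5 = 3.5%; 0.02 × 0.5 = 1.0%. Ratio 3.5, difference 2.5 points.
- Coded: 0.035 × 0.8 + 0.01 = 3.8%; 0.010 × 0.8 + 0.01 = 1.8%. Ratio 2.11, difference 2.0 points.
- Monitored counts: 70 true starts, 14 missed, 20 antiplatelet added, 76 counted.
- Control counts: 40 true starts, 8 missed, 40 antiplatelet added, 72 counted. More than half of the counted control events (40 of 72) are antiplatelet starts.

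*Which defect does what.* With warfarin omitted and p = 0, the rates are 2.8% and 0.8%: the ratio stays at 3.5 and the difference falls from 2.5 to 2.0 points. With P2Y12 added and w = 0, they are 4.5% and 2.0%: the ratio falls to 2.25 and the difference stays at 2.5 points. With equal shares in both cohorts, then, warfarin costs absolute difference and P2Y12 dilutes the ratio.

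*Anticoagulant starts for other reasons, q = 1% (prior pulmonary embolism is a qualifying condition).* Named: 4.5% and 2.0%, ratio 2.25. Coded: 4.8% and 2.8% (1.71) if all of these starts are listed agents, or 4.6% and 2.6% (1.77) if 20% are warfarin.

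*Ranges, equal in both cohorts (t 30% or 50%; w 20% or 40%; p 1%, 2% or 3%).*

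| q | Named ratio | Coded ratio |
|---|---|---|
| 0 | 3.5 | 1.27 to 2.11 |
| 1% | 1.94 to 2.25 | 1.21 to 1.77 |

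If w and p are both zero, nothing is distorted.

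*Opposite direction: warfarin share 20% monitored and 40% control, t = 50%, p = 0.* With q = 0, the coded rates are 0.035 × 0.8 = 2.8% and 0.010 × 0.6 = 0.6%, ratio 4.67 against 3.5. With q = 1% and the same shares, they are 3.6% and 1.2%, ratio 3.0 against 2.25.

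**The case against.** The best defense is that SAP section 7, which specifies the analysis, speaks only of anticoagulants. An analyst following it literally would count warfarin and leave out antiplatelets. The fills are all planned as Other Endpoints 73 and 75 to 78, and Secondary Endpoint 2 has no explicit cross-reference to analysis 5 either. Limbs a and b carry separate dates, which would permit separate reporting. The surrounding list is visibly unfinished: its numbering is out of order and the neighbouring utilization item carries an open comment. On this view only a mapping is missing.

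Part of this stands. The data are planned, and the link from endpoint 2 to analysis 5 rests on its heading and its place among the secondary endpoints. But endpoint 2 is the only drug-coded definition under that name, and a class name in section 7 does not override an explicit list. Separate dates are not a plan for separate reporting. Choosing other fields at analysis would be a decision the plan does not make.

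Three points on size also stand. The fall in the ratio in the base case comes from the P2Y12 limb, not from warfarin. Every treatment share is assumed, and the ranges shown begin at nonzero values. The planned Fisher's exact test would often still reject: at the base-case counts (76 of 2,000 against 72 of 4,000), p is about 0.000005, and across the 12 combinations with q = 0 it is below 0.05 in 11, one of them only just (0.0495). The concern is therefore with the estimate and what it means; no loss of significance or power is claimed.

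**Conclusion.** The concern holds. Followed as written, the coded endpoint misclassifies starts in both directions, and the rate reported under analysis 5 would not be the rate of anticoagulation initiation. This follows from the text and needs no assumption beyond warfarin or P2Y12-only starts occurring.

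The size is not known. Under the stated assumptions the ratio could fall from 3.5 to about 2.1, or rise to 4.67 if warfarin shares differ between cohorts. These are illustrations, not estimates.

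The scope is one of twelve secondary analyses. The primary endpoint and the 3-year clinical endpoints are untouched. It should be corrected before the 12-month analysis.

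**What to change.** - Define the analysis 5 endpoint as the first fill of any anticoagulant, including warfarin, after the start date already set in SAP section 4 for the matched cohort study. Build it from Other Endpoints 75 (novel agents) and 77 (warfarin) and from named agents within 76, and state whether heparin (78) counts.
- Report P2Y12 starts separately from item 73. If a composite is wanted, add it as a further endpoint labelled antithrombotic.
- Make SAP Secondary Endpoint 2 and protocol Endpoint Data Dictionary item 4 agree, including on the acute coronary syndrome exception, and refer to the definition from SAP section 7.
- Optionally, state a fill-free look-back period for a fill to count as new.

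The cost is wording in the two documents, since the follow-up fills are already planned fields. Only the optional look-back needs more data: baseline anticoagulant fills are not among baseline prescription items 51 to 63, and would come from the same pharmacy source. The change affects what is counted, not how anyone is treated.

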1. INTRODUCTION AND BACKGROUND

The mHealth Screening to Prevent Strokes (mSToPS) study is designed to determine whether mobile health monitoring can detect previously undiagnosed asymptomatic atrial fibrillation more effectively and lead to a reduction of thromboembolic events compared with usual care in a high-risk cohort identified and tracked using claims data.

The overarching objective of this study is to demonstrate that screening select individuals in their homes using wearable sensor technology can identify individuals with asymptomatic atrial fibrillation and that doing so will influence treatment and clinical outcomes.

Atrial Fibrillation Detection Objectives

- Identify a high-risk cohort optimized for screening based on claims data information.
- Determine the relative benefit of active screening compared to routine care (i.e., standard of care as defined by the medical care each patient is already receiving) for identifying new cases of atrial fibrillation after 4 months in the randomized cohort, and at one year in the combined monitored cohorts versus the matched observational control cohort
- As an exploratory analysis, compare the diagnostic capability of two different methods of rhythm screening – time-limited patch ECG monitoring versus long-term wearable pulse wave monitoring through photoplethysmography – for AF detection and tolerability.

Influence on Clinical Care

- Compare the rate of initiation of anticoagulation and other AF-specific therapeutic interventions (i.e. antiarrhythmic agents excluding beta-blockers and calcium channel blockers, cardioversions, ablation procedures or hospitalizations with a primary diagnosis of AF) at 12-months in the active monitoring cohort versus the matched observational control cohort.
- Compare the overall incremental costs of active monitoring for AF detection versus standard of care in the 3 years following the onset of monitoring.
- Identify the impact of active AF screening versus routine care on the time to first event of the following endpoints using claims data; A) among individuals diagnosed with new AF at 3 years following the initiation of screening, and B) the entire study cohort: utilizing claims data.
 - The combined endpoint of stroke/TIA, other systemic embolism, and/or myocardial infarction.

- In the Medicare population only, in who mortality data will be available, the combined endpoint of stroke/TIA, other systemic embolism, myocardial infarction and/or death

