We will use the same time to event analyses with 3 year follow-up to evaluate the same disease and hospitalization endpoints among the subset of subjects included in the matched observational cohort study who receive a diagnosis of atrial fibrillation during the study. All analyses will be performed as intention-to-treat with parallel exploratory analyses performed on per-protocol basis restricted to subjects enrolled in the monitoring group who underwent Zio patch monitoring.

Analysis of Safety Endpoints

For analysis of safety endpoints at 3 year follow-up, we will compare incidence of hospitalization for bleeding per person-years of follow-up between the actively monitored group and the matched observational control group. Hospitalizations for bleeding will also be characterized by length of stay. Other safety outcomes will be characterized for the period of active monitoring in the active monitoring group only. These include Incidence of non-AF, but other actionable heart rhythms captured by the Zio patch device, specifically: 1) Atrial Tachycardia with variable block of > 30 seconds; 2) Ventricular Tachycardia >5 beats; 3) Pauses \geq 5 seconds; and 4) AV block. We will also characterize early discontinuation of active monitoring in monitored cohort by cause and time to event.

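### The SAP's other AF-related therapies endpoint counts antiarrhythmics, cardioversions and ablations without an AF diagnosis, so therapy for non-AF rhythms counts too, including rhythms only the patch finds

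*SAP*

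**What the plan says.** The objective in SAP section 1 is to "Compare the rate of initiation of anticoagulation and other AF-specific therapeutic interventions" at 12 months; Protocol section 3 has the same aim. SAP section 3, Secondary Analyses item 6, turns it into an analysis: "Compare the rate of initiation of other atrial fibrillation-related therapies" in the actively monitored cohort against the matched controls. SAP section 5 gives the components: "Other AF-related therapies (i.e. antiarrhythmic agents excluding beta-blockers and calcium channel blockers, cardioversions, ablation procedures", with admissions whose primary diagnosis is AF as the fourth and last item.

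SAP section 7 (12 month Follow-up) compares proportions of whole groups, "actively monitored cohort and matched observational cohort using Fisher's exact test", and applies the same analysis to "new prescription for anticoagulation medication and new prescription of other AF-related medications". Procedures and admissions are not named there.

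On what the patch can turn up, Protocol section 4 (Atrial Fibrillation Diagnosis) states: "Individuals who are identified with AF or other actionable rhythm in the monitored cohort will be contacted". With permission, so is a provider, and Protocol section 5 adds that full patch reports are sent. SAP section 5 names four such rhythms: atrial tachycardia with variable block, ventricular tachycardia, pauses and AV block. SAP section 7 (Analysis of Safety Endpoints) describes "Incidence of non-AF, but other actionable heart rhythms captured by the Zio patch device" for the monitored group alone.

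**The concern.** The endpoint is labelled AF-specific, but three of its four components carry no AF condition, no indication and no date order relative to an AF diagnosis. A monitored subject whose patch shows ventricular tachycardia and no AF, and who then starts an antiarrhythmic, scores as having begun AF-related therapy. So does a control who gets the same drug for a rhythm found in clinic. A control with the same silent rhythm wears no patch, is told nothing, and does not score on account of it.

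This analysis is one of the direct tests of whether finding AF changes treatment. Non-AF therapy common to both cohorts blurs that test. Therapy prompted by patch findings other than AF adds to one side only. It arises after enrolment and because of the patch, so matching on age, sex and CHA₂DS₂-VASc, or adjusting for baseline covariates, cannot remove it.

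**Working it through.** **1. Text check.** In the four-part list the AF qualifier attaches to hospitalizations. Nothing elsewhere restores it for the other three parts:
- SAP section 3 item 6 compares whole cohorts.
- The AF sub-population in SAP section 4 is defined for disease endpoints and hospitalization events, not for therapies.
- SAP section 5 does write a diagnosis condition for another drug item (P2Y12 fills are counted only without a new acute coronary syndrome), but none here.

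**2. Nearest stated figure.** The plan gives no rate, effect or power for this endpoint. The cohort sizes can be checked on 12-month AF diagnosis (SAP section 7: 7% vs 2%, 2,000 vs 4,000, two-sided 0.05, power above 99%).
- Pooled rate = (140 + 80)/6,000 = 0.0367.
- Null SE = √(0.0367 × 0.9633 × (1/2,000 + 1/4,000)) = 0.00515.
- Alternative SE = √(0.07 × 0.93/2,000 + 0.02 × 0.98/4,000) = 0.00612.
- z = (0.05 − 1.96 × 0.00515)/0.00612 ≈ 6.5, so power exceeds 0.9999. The figure reproduces.

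**3. Direction.** Let a₁ and a₀ be the true AF-therapy rates (monitored, control), b the non-AF therapy rate shared by both cohorts, and e the extra rate from patch-found non-AF rhythms. Treat these as non-overlapping.
- Observed difference = (a₁ + b + e) − (a₀ + b) = (a₁ − a₀) + e. It is inflated by e whatever b is.
- Observed ratio = (a₁ + b + e)/(a₀ + b). With true ratio R = a₁/a₀, it exceeds R only if e > b(R − 1).

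Assumed inputs: 10% of AF cases receive one of these therapies, so a₁ = 7% × 10% = 0.70%, a₀ = 2% × 10% = 0.20% and R = 3.5. For e, 1–6% of monitored subjects have another reported rhythm and 5–20% of those are treated, so e = 0.05–1.2% (1 to 24 of 2,000). Only the 7% and 2% come from the plan.

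| Shared background b | Observed ratio, e = 0.05% | Observed ratio, e = 1.2% |
|---|---|---|
| 0 | 0.75/0.20 = 3.75 | 1.90/0.20 = 9.5 |
| 0.5% | 1.25/0.70 = 1.79 | 2.40/0.70 = 3.43 |
| 1% | 1.75/1.20 = 1.46 | 2.90/1.20 = 2.42 |

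The observed ratio drops below 3.5 once b exceeds 0.05/2.5 = 0.02% (low e) or 1.2/2.5 = 0.48% (high e). The difference, truly 0.50 points, reads 0.55 to 1.70 points in every row.

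**4. Chance of a false positive.** Assume every other source of these therapies gives the same base rate in both cohorts, and that some extra monitored subjects are treated for a patch-found non-AF rhythm. Simulated two-sided Fisher's exact test, 2,000 vs 4,000 independent subjects, 4,000 replicates (simulation SE at most √(0.25/4,000) = 0.8 points). Entries are the share of trials significant in favour of monitoring, with the apparent risk ratio in brackets.

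| Base rate | 0 extra | 2 extra (0.1%) | 5 extra (0.25%) | 10 extra (0.5%) | 20 extra (1%) |
|---|---|---|---|---|---|
| 0.5% | 2% | 6% (1.2) | 20% (1.5) | 54% (2.0) | 97% (3.0) |
| 1% | 2% | 4% (1.1) | 13% (1.25) | 37% (1.5) | 85% (2.0) |
| 2% | 2% | 4% (1.05) | 9% (1.12) | 23% (1.25) | 65% (1.5) |

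**The case against.** A reader might infer that the error falls in the monitored cohort only, always favours monitoring, and inflates the ratio to somewhere between 3.75 and 9.5. The documents do not support that. The rule applies to both cohorts, and a control treated for a clinically found non-AF rhythm scores too. Those ratios, and the 1.25 to 7.0 that the same inputs give if true AF therapy were equal at 0.20%, require zero shared background. At b = 1% they fall to 1.46–2.42 and 1.04–2.0. This part of the objection stands in full.

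The upper end of e is also unsupported. It applies one treated share to all four rhythms, although nothing in the documents says that pauses or AV block lead to a counted therapy. Pacemakers are a separate follow-up item in SAP section 5, and beta-blockers and calcium channel blockers are already outside the endpoint.

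SAP section 7 names medications only. Under that text the problem acts through antiarrhythmic fills alone, which narrows it but does not remove it.

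An ungated count from claims is at least ascertained alike in both cohorts, whereas Endpoint 1a (patch AF) exists only for monitored subjects. That is a fair criticism of any gate using 1a, and is the reason for the sensitivity analyses proposed below.

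Finally, all treatment prompted by screening could be called a genuine effect of screening. That would be a different endpoint and could not be reported as AF-related. Reading the AF qualifier as covering the whole list would close the gap, but the wording does not carry that for drug fills and no rule implements it.

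**Conclusion.** The concern holds in limited form. As written, the endpoint counts therapy for non-AF rhythms under an AF label. The part found clinically enters both cohorts and dilutes the ratio. The part found by the patch and reported under the protocol can enter only the monitored cohort and inflates the absolute difference in its favour.

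The size cannot be derived from the documents, and the net direction on the ratio scale depends on an unknown background. The simulation shows only that, if these therapies are rare, 10 to 20 such subjects among 2,000 could produce a sizeable false effect, while 2 would hardly matter. All therapy rates behind that statement are assumed.

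This is one of twelve secondary analyses. The anticoagulation comparison (item 5) does not use this list. The change is worth making because it is cheap.

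**What to change.** - For SAP section 3 item 6, SAP section 5 and the 12-month analysis in SAP section 7, count an antiarrhythmic fill, cardioversion or ablation as AF-related only if the subject has an AF/flutter diagnosis (Endpoint 1a or 1b) on or before the therapy date, or within a short fixed window after it (30 days, for example) to allow for claim timing.
- Keep whole-cohort denominators, so that no subset is selected on a post-enrolment event.
- Report two sensitivity analyses: the ungated count, and a version gated on a claims diagnosis alone, which is measured the same way in both cohorts.
- Tabulate therapies without an AF diagnosis separately, next to the non-AF actionable rhythms.
- Reconcile SAP sections 3 and 5 (drugs, procedures and AF admissions) with SAP section 7 (medications only).

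The cost is SAP wording and one date condition. AF diagnosis, antiarrhythmic fills, cardioversion and ablation are already follow-up variables in SAP section 5. Dates are listed there for AF but not for these therapies, so they should be added; a 12-month initiation endpoint needs them anyway.

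Three downsides remain. Endpoint 1a is available only in the monitored cohort. Some AF therapy with no coded AF diagnosis moves to the separate table. Therapy for another rhythm still counts in a subject who also has AF, so most but not all of the excess is removed.
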